5.1. Primary Objective

The primary objective is to compare overall survival (OS) for ramucirumab versus placebo in patients with advanced hepatocellular carcinoma (HCC) and elevated baseline alpha-fetoprotein (AFP) after intolerance or progression on prior sorafenib treatment.

5.2. Secondary Objectives

The secondary objectives of the study are to evaluate:

- Progression-free survival (PFS)
- Time to radiographic progression (TTP)
- Objective response rate (ORR)
- Safety profile of ramucirumab
- Ramucirumab pharmacokinetics (PK)
- Immunogenicity of ramucirumab
- Time to deterioration in Functional Assessment of Cancer Therapy (FACT) Hepatobiliary Symptom Index-8 (FHSI-8)
- Time to deterioration in Eastern Cooperative Oncology Group performance status (ECOG PS)
- Patient-reported outcome (PRO) measures of disease-specific symptoms and health-related quality of life

5.3. Exploratory Objectives

The exploratory objective of the study is to explore biomarkers relevant to ramucirumab, angiogenesis, and the disease state and to correlate these markers to clinical outcome.

6. A Priori Statistical Methods

6.1. Introduction

This SAP describes the detailed procedures for executing the planned statistical analyses in order to assess the efficacy and safety profile of ramucirumab when administered to patients with HCC after first-line therapy with sorafenib. The statistical analyses will be conducted by Eli Lilly or a contract research organization using SAS® software Version 9.2 or higher.

6.2. Study Design

Study I4T-MC-JVDE (JVDE) is a global, multicenter, randomized, double-blind, placebo-controlled Phase 3 study evaluating the efficacy and safety of ramucirumab as a single agent for the treatment of patients with advanced HCC and elevated baseline AFP after intolerance or progression on prior sorafenib therapy. Patients with a baseline AFP ≥ 400 ng/mL, based on local laboratory results, who meet all other inclusion/ exclusion criteria will be randomized. The study will randomize (in a 2:1 ratio) approximately 279 patients to receive ramucirumab 8 mg/kg or placebo administered intravenously once every 14 days in an outpatient setting. Randomization will be stratified by the following factors:

- geographic region (Region 1 versus Region 2 versus Region 3)
- macrovascular invasion (yes versus no)
- Eastern Cooperative Oncology Group (ECOG) performance status (PS) (0 versus 1)

All patients will be offered best supportive care (BSC), as determined appropriate by the investigator. Study treatment will be continued until disease progression, unacceptable toxicity, withdrawal of consent, or until other withdrawal criterion is met.

During study, tumor assessment and imaging will be performed as follows:

- every 6 weeks (± 3 days) for the first 6 months after randomization, and
- every 9 weeks (± 3 days) thereafter until the patient has radiographic progressive disease (PD) or dies, whichever occurs first.

During long-term follow-up, the patient will be followed up approximately every 60 days (± 7 days) until death or study completion, whichever occurs first.

The final analysis will be performed after approximately 221 deaths have been observed.

Adverse event (AE) information will be collected until approximately 30 days after the patient and the investigator agree that the patient will no longer continue study treatment and until all SAEs related to protocol procedures or study treatment have resolved or been explained.

6.2.1. Region and Country

The general plan for assigning participating countries to a geographic region is as follows:

1. Region 1 will include countries in the Americas, Europe, Israel, and Australia.

2. Region 2 will include countries in Asia, except for Japan.
3. Region 3 will include Japan only.

Table 1 below shows the planned countries (country with at least 1 randomized patient) and corresponding regions under which they will be grouped for data analyses:

Table 1. Countries in Each Geographic Region used for Stratification and Data Analyses

Region Number	Country
Region 1	Brazil
	Canada
	United States
	Australia
	Austria
	Belgium
	Czech Republic
	Poland
	France
	Germany
	Israel
	Italy
	Spain
	United Kingdom
	Switzerland
Region 2	Korea
	China
	Hong Kong
	Taiwan
Region 3	Japan

6.2.2. Determination of Sample Size

The primary objective of this study is to compare ramucirumab versus placebo in terms of OS in patients with advanced HCC after intolerance or progression on prior sorafenib. The sample size was determined based on the following assumptions:

- hazard ratio (treatment/control) of 0.67, with median OS of 4.5 months in the placebo arm and 6.7 months in the ramucirumab arm
- the randomization ratio is 2:1 (ramucirumab:placebo)
- the overall significance level will be controlled at 1-sided 0.025 (2-sided 0.05)
- the Type II error rate is 20%; that is, the statistical power of the trial is set to 80%

Under the assumptions above, the final analysis will be performed when at least 221 deaths have been observed. Therefore, the study will randomize approximately 279 patients (that is, 20% censoring rate including dropouts, with approximately 186 patients randomized to the ramucirumab arm and 93 patients randomized to the placebo arm).

6.3. Analysis Populations

6.3.1. *Intent-to-Treat (ITT) Population*

The ITT population will comprise all randomized patients. This population will be assessed for baseline characteristics and efficacy including quality of life (QoL). The ITT analysis of these data will consider allocation of patients to treatment groups as randomized regardless what actual treatment they receive.

6.3.2. *Safety Population*

The Safety population will include all patients who received at least 1 dose (including a partial dose) of an investigational product (ramucirumab or placebo). Analysis of safety data will be based on the Safety population and will be performed based on the actual treatment a patient received on the first study treatment administration regardless of which treatment they were randomized to receive (“as treated”).

6.3.3. *Per-Protocol (PP) Population*

Per-protocol population will include all patients who are randomized and treated and do not have any major protocol violations that could potentially affect the efficacy conclusions of the study. Efficacy analyses will also be performed in the PP population. The PP population is a subset of the ITT population that will be defined and finalized prior to database lock for the final analysis. Patients who meet any of the following criteria will be excluded from the PP population:

- Randomized but never received study medication
- All AFP < 400 ng/mL prior to first dose, as determined by local and/or central laboratory testing [per Inclusion Criterion (IC) 9]
- Baseline Child-Pugh (CP) score was not 5 or 6 (CP class A) [per IC 7]
- Patient does not have HCC that is Barcelona Clinic Liver Cancer (BCLC) Stage B or C at randomization [per IC 8]
- Did not have a diagnosis of HCC as defined in the protocol [per IC 1 and EC 17]
- Had not been treated with sorafenib
- Had an ECOG PS score of 2 or above at enrollment [per IC 10]
- Received any previous systemic therapy with vascular endothelial growth factor (VEGF) inhibitors or VEGF receptor inhibitors (including investigational agents) other than sorafenib for treatment of HCC [per Exclusion Criterion 23]
- Received additional concurrent chemotherapy, biological response modifiers, other investigational agents, and radiation therapy (except for palliation to symptomatic sites of disease) during the study treatment
- The patient has a history of or current hepatic encephalopathy (any grade) or current ascites (Grade ≥ 2)
- Patient received incorrect study medication at least 25% of the total number of infusions (that is, Number of incorrect medication infusions/Total number of infusions patient received $\geq 25\%$)

6.4. Definitions and Data Handling Conventions

6.4.1. Safety Definitions and Data Handling

6.4.1.1. Treatment-Emergent Adverse Events (TEAE)

Treatment-emergent adverse event (TEAE) is defined as any untoward medical occurrence that either occurs or worsens at any time after treatment baseline and that does not necessarily have to have a causal relationship with this treatment.

6.4.1.2. Adverse Events of Special Interest (AESIs)

Adverse events of special interest (AESIs) are AEs thought to be potentially associated with the study drug or the disease under study. Therefore, aggregate AE terms for AEs typically associated with anti-angiogenesis or possibly associated with the study drug were developed.

Adverse events of special interest may be modified as the understanding of the safety of the investigational drug increases. Please refer to the Investigator's Brochure update for most up-to-date aggregate AE terms. The Medical Dictionary for Regulatory Activities (MedDRA™) preferred terms (PTs) that are grouped under each of the AESI terms will be provided in the compound-level safety document.

6.4.1.3. Consolidated Adverse Events

Given the high level of granularity of the MedDRA dictionary, clinically identical or synonymous PTs reported under different terms in the database, in addition to being reported separately, will also be consolidated in a separate summary. The list of consolidated AE categories will be reported in the clinical study report.

6.4.1.4. Previous/Concomitant Medications

A medication will be regarded as **previous** if:

- the medication was stopped prior to first dose of study treatment (either ramucirumab or placebo) (medication stop date < the date of first dose of study treatment).

A medication will be regarded as **concomitant** if:

- the medication was started on or after the date of first dose of study treatment and before the end of short-term follow-up; or
- the medication was started prior to first dose of study treatment but was ongoing at the time of the first dose of study treatment.

6.4.1.5. Partial Data for Adverse Events and Previous/Concomitant Medications

For the patient data listings, no imputation of incomplete data will be applied. The listings will present the data as entered on electronic case report form (eCRF).

Dates missing the day or both the day and month of the year will adhere to the following conventions:

- If the onset date of an AE or start date of a medication is missing the day, the onset date will be set to:
 - first day of the month that the event occurred, if the onset yyyy-mm is after the yyyy-mm of first study treatment
 - the day of the first study treatment, if the onset yyyy-mm is the same as yyyy-mm of the first study treatment
 - the date of informed consent, if the onset yyyy-mm is before the yyyy-mm of the first study treatment
- If the resolution date of an AE or end date of a medication is missing the day, the resolution date will be set to:
 - the last day of the month of the occurrence
 - if the patient died in the same month, then set the imputed date as the death date
- If the onset date of an AE or start date of a medication is missing both the day and month, the onset date will be set to:
 - January 1 of the year of onset, if the onset year is after the year of the first study treatment
 - the date of the first treatment, if the onset year is the same as the year of the first study treatment
 - the date of informed consent, if the onset year is before the year of the first study treatment
- If the resolution date of an AE or end date of a medication is missing both the day and month, the date will be set to:
 - December 31 of the year of occurrence
 - if the patient died in the same year, then set the imputed date as the death date

If onset date is completely missing, then no imputation will be done and the event will be considered as treatment emergent (for AEs) or concomitant (for medications) unless the end date rules out the possibility.

For all dates prior to signing informed consent form (ICF), the following conventions will be used for imputing partial dates:

- if only the day of the month is missing, use 1st of the month
- if both the day and the month are missing, use 01 January

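### SAP 6.4.1.5 sets a partial onset date to the first-dose date without checking the end date, so some AEs that resolved before treatment count as treatment-emergent

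*SAP*

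**What the plan says.** SAP 6.4.1.5 has four rules that matter here.

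- Day missing: the onset or start becomes "the day of the first study treatment, if the onset yyyy-mm is the same as yyyy-mm of the first study treatment". If the known month is earlier than the first-dose month, the consent date is used instead.
- Day and month missing: the onset or start becomes "the date of the first treatment, if the onset year is the same as the year of the first study treatment".
- Whole date missing: "If onset date is completely missing, then no imputation will be done and the event will be considered as treatment emergent", and a medication is taken as "concomitant (for medications) unless the end date rules out the possibility".
- Dates before consent: a separate convention, opening "For all dates prior to signing informed consent form (ICF), the following conventions will be used for imputing partial dates", uses the first of the month or 1 January.

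The same section says that patient listings show dates as entered, without imputation.

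SAP 6.4.1.1 defines a TEAE as an event that "either occurs or worsens at any time after treatment baseline". SAP 6.4.1.4 calls a medication *previous* if "the medication was stopped prior to first dose of study treatment". Its first *concomitant* criterion depends on a start date at or after the first dose and sets no condition on the stop date.

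**The concern.** The SAP accepts that a known end date can rule out treatment emergence, but it uses that information only when nothing at all is known about onset. When the month or year of onset is known, the end date is ignored. A record with more information is thus handled less accurately than one with less.

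An event that ended before the first infusion can neither begin nor worsen on treatment. Under the rule as written it can still enter the TEAE tables, with an imputed onset later than its own resolution. For medications the result is a record that satisfies two categories a reader would expect to be exclusive. At stake are the TEAE and concomitant-medication counts, and whether programmers have to settle impossible dates case by case.

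**Working it through.** The plan states no figure to reproduce. The check applies the written rules to constructed dates.

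**Inputs**
- Onset and start imputation, the end-date check and the pre-consent rule: SAP 6.4.1.5.
- *Previous* and *concomitant* definitions: SAP 6.4.1.4.
- TEAE definition: SAP 6.4.1.1. Safety baseline, the latest available value before the first infusion: SAP 6.4.3. The SAP writes out no date comparison for TEAEs; I take onset on or after the first-dose date as treatment-emergent, since imputing to that date would otherwise do nothing.
- Duration = end − start + 1: SAP 6.4.3.
- AEs are recorded from consent (Protocol 10.3.1), and medications from 30 days before randomization (Protocol Attachment 1). Screening starts up to 21 days before randomization (Attachment 1), and the first dose should follow within 7 days (Protocol 9.4). That gives roughly 21 + 7 = 28 days. It is not a hard limit, because 9.4 allows a later first dose after repeat laboratory tests and discussion with the sponsor's physician.

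**Constructed cases (all 2016)**

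| Case | Known onset | Consent | End | First dose | Imputed onset | End − onset + 1 | TEAE as written | TEAE with end-date check |
|---|---|---|---|---|---|---|---|---|
| A | March, day missing | 2 Mar | 12 Mar | 20 Mar | 20 Mar | −7 days | yes | no |
| B | 2016, day and month missing | 10 May | 20 May | 1 Jun | 1 Jun | −11 days | yes | no |
| C | February, day missing | 25 Feb | 12 Mar | 20 Mar | 25 Feb (consent) | 17 days | no | no |

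A and B fail: the event ended 8 and 12 days before the first dose, yet it is classed as treatment-emergent. C is handled correctly because its onset month is earlier than the first-dose month.

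**Medications.** With the dates of A or B, the imputed start equals the first-dose date, so the first *concomitant* criterion is met. The known stop date is before the first dose, so *previous* is met too. In C only *previous* is met.

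**When the rule can bite.** Three conditions must hold together: the onset is partial and its known month (or its year, if the month is missing) matches that of the first dose; the end date is on or after consent; and the end date is before the first dose. An end date with a missing day is itself moved to the end of its month, so in practice the end must be known to fall before the first dose.

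**How often the month matches.** Assume onsets are spread evenly over the g days before the first dose, and take every first-dose date in 2016. Over the 366·g onset dates, 12·g(g+1)/2 fall in an earlier month, so

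share in the same month = 1 − 12·g(g+1)/2 ÷ (366·g) = 1 − (g+1)/61.

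- g = 7: 1 − 8/61 = 87%
- g = 14: 1 − 15/61 = 75%
- g = 21: 1 − 22/61 = 64%
- g = 28: 1 − 29/61 = 52.5%

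These are shares of day-missing onsets that meet the month condition only. They are not rates of misclassified records, because the documents give neither the rate of partial dates nor the share of such events that ended before the first dose.

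**The case against.** The strongest reply is that imputing toward the first dose is a deliberately cautious convention, that the TEAE definition itself excludes an event already over, and that the clause "unless the end date rules out the possibility" shows the authors meant to respect end dates. Part of this stands: the intent is clear, and a careful programmer might apply it. But caution is a reason to impute toward treatment when emergence is uncertain, and here the recorded end date removes the uncertainty. The clause belongs to the sentence on completely missing dates and does not reach the partial-date rules.

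A reader might also infer more than the documents support:

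- *That every partially dated AE resolved before treatment is misclassified.* It is not. Onsets in an earlier known month go to the consent date (case C), and records lying wholly before consent have their own rule.
- *That negative AE durations would be reported.* Protocol 12.2.11 puts AE durations in listings, and SAP 6.4.1.5 keeps listings free of imputation. The −7 and −11 days show that the derived dates are impossible; they are not a planned result.
- *That a stopped drug changes from previous to concomitant.* It stays *previous* by its stop date and meets *concomitant* as well.
- *That a definite fraction of patients is affected.* Collecting AEs from consent makes such records possible; it does not show how many there are.

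**Conclusion.** The gap is real but minor. Two stated imputation rules give a wrong answer for a narrow set of records: partial onset or start in the first-dose month (or year, if the month is missing), with a known end after consent and before the first dose. For AEs the consequence is a false TEAE in the summary tables; for medications it is double classification with no precedence.

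The rule is the same in both arms, and these events precede treatment, so there is no reason to expect it to favour either one. OS, PFS and the other efficacy analyses do not use these dates. The size cannot be computed from the documents. The conclusion rests on the literal text of SAP 6.4.1.5 and on the TEAE flag being taken from the imputed onset, with the first-dose date counting as on treatment.

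**What to change.** In SAP 6.4.1.5, extend the existing end-date check to onset and start dates that are only partly missing. If the end date is before the first study treatment, the AE is not treatment-emergent, and the imputed onset may not be later than the end date. In SAP 6.4.1.4, state that a medication stopped before the first dose is *previous* only.

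The cost is about a sentence in each section and a line of derivation code. No efficacy analysis, error rate or data collection changes.

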6.4.1.6. Study Drug Exposure

Exposure analyses will be based on the actual dose administered (in mg) and body weight (in kg) at each treatment cycle.

Ramucirumab /Placebo Treatment:

- Number of infusions

- Duration of treatment (weeks) = [(Date of last dose – date of first dose)+14]÷7
Note: 14 days added to duration of treatment because administration is every 2 weeks [on Day 1 of each 2-week cycle]

Cumulative dose, dose intensity, and relative dose intensity:

- Cumulative dose (mg/kg) = Sum of all (total doses administered [mg] ÷ Last available weight [kg] prior to each dosing)
- Dose intensity (mg/kg/week) = (Cumulative dose) ÷ (Duration of treatment)
- Planned weekly dose intensity (mg/kg/week) = 8 mg/kg / 2 weeks = 4 mg/kg/week
- Relative dose intensity (%) = (Dose intensity) ÷ (Planned weekly dose intensity) x 100.

Number of dose reductions: total number of reduction steps considering the intended dose level before each infusion (as entered in the eCRF) as referenced in [Table 2](#) below.

Table 2. Dose Reductions for Ramucirumab

Dose Level	Ramucirumab
	8 mg/kg
Reduction to first dose level	6 mg/kg
Reduction to second dose level	5 mg/kg

The protocol stipulates that study treatment be administered every 14 days ± 3 days. Hence, the minimum interval between 2 dose administrations is 11 days (14-3 days). For purposes of analysis, the number of dose delays and dose omissions will be defined as follows:

- **Number of Dose delay:** Total number of treatments reported as delayed in CRF that were administered >3 days but ≤ 11 days beyond a scheduled infusion where treatment not given.
- **Number of Dose omitted (Not Administered):** Total number of treatments reported as omitted or delayed in CRF that were administered >11 days beyond a scheduled infusion where treatment not given.

6.4.2. Efficacy Definitions and Data Handling

6.4.2.1. Overall Survival

The OS time is defined as the time from the date of randomization to the date of death from any cause. If a patient is not known to have died on or before the date of data cut-off, OS data will be censored on the last date (on or before the cut-off date) the patient was known to be alive.

6.4.2.2. Progression-Free Survival

Progression-free survival is defined as the time from the date of randomization until the date of objectively determined PD or death from any cause. Censoring rules for the PFS main analysis are described in [Table 3](#).

Table 3. Censoring Rules for PFS – Main Analysis

Situation	Event / Censor	Date of Event or Censor
Tumor progression or death	Event	Earliest date of PD or death
No tumor progression and no death	Censored	Date of last adequate radiological assessment or date of randomization (whichever is later)
unless		
No baseline radiological tumor assessment available	Censored	Date of randomization
No adequate post baseline radiological tumor assessment available and death reported after 2 scan intervals following randomization	Censored	Date of randomization
New anticancer treatment started and no tumor progression or death within 14 days	Censored	Date of adequate radiological assessment prior to (start of new therapy +14 days) or date of randomization (whichever is later)
Tumor progression or death documented immediately after 2 or more scan intervals following last adequate radiological tumor assessment or randomization (whichever is later)	Censored	Date of last adequate radiological assessment or date of randomization (whichever is later)

Abbreviations: CR = complete response; PD = progressive disease; PFS = progression-free survival; PR = partial response; SD = stable disease.

Notes:

1. Clinical progression (that is, symptomatic progressions, which are not radiologically confirmed) will not be considered as progressions.
2. Adequate radiological tumor assessment refers to an assessment with one of the following responses: CR, PR, SD, or PD.
3. If target, non-target and new lesion assessments have different dates within a visit, then the earliest of those dates will be considered as the date of the tumor assessment if the assessment for that visit is PD; otherwise, the latest date will be used.

The censoring rules used for sensitivity analyses on PFS will be the same as the PFS main analysis above except the one alternative rule as listed below in [Table 4](#) for each analysis.

Table 4. Censoring Rules for PFS – Sensitivity Analyses

Sensitivity Analysis	Situation	Date of Progression or Censor	Outcome
Count clinical progression as progression	Documented progression or clinical progression	Date of documented progression (New Lesion, Unequivocal Progression of Non-Target Lesion, or Progression of Target Lesion). If a tumor assessment was performed on multiple days, use the earliest date for that visit. Or date of clinical progression, whichever occurred first.	Progressed
Ignore new anticancer treatment	New therapeutic anticancer treatment started prior to documented progression or death	Date of progression or death based on subsequent tumor assessments	Progressed
Ignore missing tumor assessments	Death or documented progression after \geq two consecutively missed tumor assessment visits	Date of first scheduled tumor assessment within the time period of the consecutively missed visits	Progressed
Treat lost to follow up as progression (worst case scenario)	Patient lost to follow-up without documented progression or death	Date of next scheduled tumor assessment after last tumor assessment	Progressed

Abbreviation: PFS = progression-free survival.

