6.4.2.6. Time to Radiographic Progression

Time to radiographic progression (TTP) is defined as the time from the date of randomization until the date of radiographic progression according to RECIST 1.1. Censoring rules are described in [Table 5](#).

Table 5. Rules for Determining Date of Progression or Censor for TTP

Situation	Event / Censor	Date of Event or Censor
Tumor progression	Event	Earliest date of PD
No tumor progression (regardless of death)	Censored	Date of last adequate radiological assessment or date of randomization (whichever is later)
unless		
No baseline radiological tumor assessment available	Censored	Date of randomization
No adequate post baseline radiological tumor assessment available	Censored	Date of randomization
New anticancer treatment started and no tumor progression within 14 days	Censored	Date of adequate radiological assessment prior to (start of new therapy +14 days) or date of randomization (whichever is later)
Tumor progression documented immediately after 2 or more scan intervals following last adequate radiological tumor assessment or randomization (whichever is later)	Censored	Date of last adequate radiological assessment or date of randomization (whichever is later)

Abbreviations: CR = complete response; PD = progressive disease; PFS = progression-free survival; PR = partial response; SD = stable disease.

Notes:

1. Clinical progression (that is, symptomatic progressions, which are not radiologically confirmed) will not be considered as progressions.
2. Adequate radiological tumor assessment refers to an assessment with one of the following responses: CR, PR, SD, or PD.
3. If target, non-target and new lesion assessments have different dates within a visit, then the earliest of those dates will be considered as the date of the tumor assessment if the assessment for that visit is PD; otherwise the latest date will be used.

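### Two override rows in the SAP's PFS censoring table (one repeated for TTP) are worded so that a known event can become a censored time

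*SAP*

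**What the plan says.** SAP 6.4.2.2 opens with the definition: "Progression-free survival is defined as the time from the date of randomization until the date of objectively determined PD or death from any cause". Table 3 has an event row, dated "Earliest date of PD or death", and a row for patients with neither event. Four rows under an unless heading follow, and all four end in censoring. Three of them matter here:

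- "No baseline radiological tumor assessment available": censored at randomization, with no condition on what happens later.
- No adequate post-baseline scan: censored at randomization only with "death reported after 2 scan intervals following randomization". A death before that point stays an event.
- "New anticancer treatment started and no tumor progression or death within 14 days": censored at the adequate scan before the start of new therapy plus 14 days, or at randomization if later.

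Note 2 to the table reads: "Adequate radiological tumor assessment refers to an assessment with one of the following responses: CR, PR, SD, or PD". A progression scan is therefore an adequate scan.

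Table 5 (SAP 6.4.2.6) repeats the new-therapy row for TTP: "New anticancer treatment started and no tumor progression within 14 days". In Table 4, the sensitivity analysis that ignores new treatment describes its case as "New therapeutic anticancer treatment started prior to documented progression or death". Each Table 4 analysis otherwise keeps the main rules. SAP 6.5.3.3 makes PFS the first endpoint tested after OS.

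**The concern.** The rows under the unless heading have to override the event row. Two of them describe a progression or death that has happened and still end in censoring. Any such row that is worded too broadly can therefore turn a known event into a censored time.

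The no-baseline row does this for deaths. Dating a death needs no baseline scan, and the adjacent row treats the same early death the opposite way.

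The new-therapy row can do it for progressions, because it sets no order between therapy and progression. The path is foreseeable. Progression is a reason to stop treatment (protocol 7.3.2), other systemic anticancer therapy is barred until then (9.6), and later therapy is recorded (10.1.2). SAP 6.5.4 itself considers that such therapy may differ between arms.

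If the literal rule were programmed, the first gated secondary endpoint would lose events, and its hazard ratio could shift.

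**Working it through.** **Design figures.** The plan gives no PFS event count or PFS power, so the OS figures are the only ones to reproduce. Inputs from SAP 6.2.2: HR 0.67, 2:1 allocation, 2-sided 0.05, 80% power.

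- Events = (1.960 + 0.842)² / [(2/3)(1/3)(ln 0.67)²] = 7.849 / 0.03564 = 220.2, so 221, as stated.
- Patients = 221 / 0.80 = 277, against 279 stated.

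These agree and are not in dispute.

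**No-baseline row.** Take a death on day 50 with no earlier progression. Two 6-week scan intervals are 84 days.

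- Baseline scan present, no post-baseline scan: 50 < 84, so it is an event on day 50.
- No baseline scan: censored at randomization.

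None of the four Table 4 analyses changes the second result.

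**New-therapy row.** The literal reading asks only whether progression or death falls in the 14 days after therapy starts. The other reading asks whether either has occurred by the end of those 14 days.

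| PD day | Therapy day | Literal | PD by therapy start + 14 counts |
|---|---|---|---|
| 42 | none | event, day 42 | event, day 42 |
| 42 | 63 | censored, day 42 | event, day 42 |
| 42 | 50 | censored, day 42 | event, day 42 |
| 90 | 80 | event, day 90 | event, day 90 |
| 126 | 63 | censored, last scan before day 77 | same |

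The censoring date in the second and third lines is the PD scan itself: note 2 makes it adequate, and protocol 10.1.2 requires no scans after radiographic progression. Table 4 as worded covers therapy begun before progression, so it does not reach these two patients. The other sensitivity analyses inherit the main rule.

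**Size under the literal reading.** Let q be the share of an arm's PFS events converted to censored times. It is not in the documents and is varied here as an assumption. If conversion does not depend on event time, time at risk is unchanged and the hazard is multiplied by (1 − q). The HR is then multiplied by (1 − qR)/(1 − qP), and an exponential median by 1/(1 − q).

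Equal q, with an assumed PFS HR of 0.67 and 250 events E before conversion; power = Φ(|ln HR|·√(2E(1 − q)/9) − 1.96):

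| q | Events left | Median factor | Power |
|---|---|---|---|
| 0% | 250 | 1.00 | 84.7% |
| 10% | 225 | 1.11 | 80.8% |
| 20% | 200 | 1.25 | 76.1% |
| 30% | 175 | 1.43 | 70.5% |
| 40% | 150 | 1.67 | 63.8% |

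Unequal q:

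- 20% ramucirumab, 30% placebo: 0.80/0.70 = 1.14, so 0.67 becomes about 0.77.
- 30% ramucirumab, 20% placebo: 0.70/0.80 = 0.875, so 0.67 becomes about 0.59.

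A simulation of 400 trials per scenario (186 and 93 patients, exponential times, assumed placebo median 1.9 months) gave HRs of 0.67 with no conversion, 0.67 with 30% in both arms, and 0.76 and 0.59 for the two unequal cases.

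**The case against.** The intended rule for new therapy can be recovered from the SAP. Table 4 describes the matching case as therapy begun before progression or death. The date cell in Table 3 counts the 14 days from the start of therapy, so the phrase can be read as no event by that date. On that reading an earlier progression stays an event. A rule that labels a progression scan as its own censoring date also looks like a misreading. This stands as evidence of intent, and a programmer may well implement it that way. It does not put the missing condition into Tables 3 and 5, and if the literal rule were used, Table 4 would not expose it.

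On the no-baseline row, a measurable lesion is an inclusion criterion (protocol 7.1) and baseline imaging is planned for every patient (10.1.1), so the row should be almost empty. That stands on size. The row is nevertheless explicit and conflicts with the PFS definition.

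A reader might infer that the plan deliberately censors ordinary progressors, or that most patients follow this path. The documents do not support either: Table 4 points the other way, no next-line rate is given, and protocol 8.2 notes that no standard of care exists in this setting. A loss computed by applying a share to 279 would also be unfounded, because 279 is the number randomized and not a PFS event count.

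**Conclusion.** The point holds as a wording defect that should be corrected in the rules for the first gated secondary endpoint. The no-baseline row of Table 3 is an explicit rule that drops early deaths; it probably touches few patients, and the documents give no count. The new-therapy rows of Tables 3 and 5 leave out the order of therapy and progression, so two readings give the same patient opposite event status.

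The HR, median and power figures apply only to the literal reading and rest on assumed values of q, the PFS HR and the event count. They show direction and scale and do not forecast bias. With equal conversion the HR is about unchanged; with unequal conversion it can move towards or away from 1.

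A reader might extend the lost-death problem to Table 5. It does not apply there, because death is not a TTP event. The OS analysis and its sample size are untouched.

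**What to change.** Change three cells in the SAP:

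- Table 3, new-therapy row: *New anticancer treatment started before any PD or death, and no PD or death up to 14 days after its start.* The censoring date stays as it is.
- Table 5, new-therapy row: the same change, for PD only.
- Table 3, no-baseline row: *censored at randomization unless the patient died within 2 scan intervals of randomization (event at date of death).* This matches the row below it.

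Confirm that the PFS and TTP derivation programs follow the same reading. The wording largely reuses the condition in Table 4 and the adjacent row of Table 3. The change needs no new data and does not alter the design or the OS analysis.
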